7.2 Statistical Methods

The primary end point is the number of migraine days per month during treatment with metformin vs placebo. The secondary end point is the percentage of patients with >50% reduction in migraine days per month (response rate). Mean 4-week migraine frequency for patients receiving metformin vs placebo treatment will be assessed by using the Hills-Armitage method. Response rate will be assessed by using the McNemar test. The frequency of adverse events during metformin treatment will be compared to that during placebo treatment by using the McNemar test.

Descriptive Statistics

Univariate descriptive statistics and frequency distributions will be calculated, as appropriate for all variables.

Handling of Missing Data

Patients will be included in the primary analysis on the basis of intention to treat. Migraine frequency will be calculated using all available follow-up data and converted to units of frequency per four weeks.

Multiplicity

There is a single primary outcome measure. If the primary analysis is statistically significant, the secondary outcome measure will be assessed in order to facilitate interpretation of clinical importance.

Interim Analysis

There will be no interim analysis for early stopping due to efficacy.

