1.5 Dose Rationale and Risk/Benefits

Metformin is a widely available, safe drug used to treat diabetes mellitus; it also is a powerful activator of AMPK. Preclinical data demonstrates efficacy of metformin in animal models of migraine, suggesting that it blocks hyperalgesia and the transformation to chronic pain.

Metformin has been studied in oncologic research as a novel anticancer drug for many types of cancers including prostate, breast, ovarian, and endometrial cancer. Many studies of metformin in nondiabetic patients with cancer have shown tolerability and lack of hypoglycemia at therapeutic doses up to 1,500 mg daily (Dilokthornsakul, 2013; Laskov, 2014).

2 Study Objectives

Study Objective 1: To compare the reduction in the number of migraine days per month during 12 weeks of treatment with metformin vs placebo (primary end point).

Hypothesis: Metformin treatment will significantly reduce the number of migraine days per month compared with placebo.

Study Objective 2: To compare the response rate (percentage of patients with a >50% reduction in migraine days per month) during 12 weeks of treatment with metformin vs placebo (secondary end point).

Hypothesis: The response rate to metformin will be significantly greater than the response rate to placebo.

Study Objective 3: To determine the safety and tolerability of metformin in patients with migraine.

Hypothesis: Metformin treatment will be safe and well tolerated, with limited adverse effects.

3 Study Design

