3.1 General Design

We will obtain approval from the Mayo Clinic Institutional Review Board, and all patients will provide written, informed consent before study enrollment.

This will be a single-center, double-blind, randomized, placebo-controlled, crossover study.

After study enrollment, patients will be randomized to the Metformin study drug group or the placebo group. The Principal Investigator or patient can't choose the study group. The patient will have an equal chance of being assigned to the Metformin group. Neither the patient or the Principal Investigator will know which study group they are participating in. In case of an emergency, this information will be available.

Patients will undergo a 2-hour oral glucose tolerance test to confirm the absence of diabetes mellitus. Subjects will then keep a paper headache diary for 4 weeks to establish baseline characteristics, including number of migraine days per month, number of moderate to severe headache days per month, and number of days per month of acute medication use. The 4-week baseline period will be followed by 2 treatment periods of 12 weeks each, separated by a

washout period of 4 weeks (total study duration, 32 weeks). During the washout period, we will washout the study drug x 4 weeks.

For the 12-week treatment periods, subjects will receive either metformin 500mg twice daily or matching placebo twice daily. During the first week of each 12 week treatment period, patients will receive metformin 250mg twice a day or matching placebo. At week 2, the dose will be increased to metformin 500mg twice a day or matching placebo. In case of intolerable side effects, the dose will be reduced to 250mg twice a day.

Subjects will have 7 clinic visits. Routine laboratory studies and a pregnancy test will be performed at enrollment and week 20. Abnormal kidney or liver function will exclude subjects. Pregnancy will exclude subjects. General and neurologic examinations will be performed during 2 of the 7 visits. At each visit, subjects will receive medication for the period until the next visit. A paper headache diary will be used for the trial. For every day that the subject has a headache of any type, she or he will record headache characteristics, associated features, and medications used.

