3.4 Primary Safety Endpoints

To determine the safety and tolerability of metformin in patients with migraine.

Hypothesis: Metformin treatment will be safe and well tolerated, with limited adverse effects.

4 Subject Selection Enrollment and Withdrawal

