7.1 Sample Size Determination

This will be a single-center, double-blind, randomized, placebo-controlled, crossover study. Crossover designs have been used successfully in migraine trials (Olesen, 1981). Prior migraine trials have suggested that a sample size of 34 patients has 80% power to detect a mean reduction in migraine days of 1.25 days per month, with $\alpha=0.05[Q^1]$ (σ 2.5, ρ 0.5; Hauge, 2009; Silberstein, 2004; Sorensen, 1986). We will enroll 40 subjects to account for an estimated 15% dropout rate.

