8.5 Medical Monitoring

It is the responsibility of the Principal Investigator to oversee the safety of the study at his/her site. This safety monitoring will include careful assessment and appropriate reporting of adverse events as noted above, as well as the construction and implementation of a site data and safety-monitoring plan (see section 10 “Study Monitoring, Auditing, and Inspecting”). Medical monitoring will include a regular assessment of the number and type of serious adverse events.

9 Data Handling and Record Keeping

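### Objective 3 hypothesises that metformin is safe and well tolerated, but the only comparative safety analysis is a McNemar difference test with no interval or criterion, which cannot support that hypothesis

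*Combined protocol and SAP*

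**What the plan says.** Section 2 states Objective 3 as a hypothesis: "Hypothesis: Metformin treatment will be safe and well tolerated, with limited adverse effects". Section 3.4 repeats it as the primary safety endpoint, described only as "To determine the safety and tolerability of metformin in patients with migraine". Neither section defines a measured variable, an acceptable event rate or a margin.

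The comparative analysis is a single sentence in Section 7.2: "The frequency of adverse events during metformin treatment will be compared to that during placebo treatment by using the McNemar test". It does not say whether the test is exact, continuity-corrected or uncorrected. It does not say whether the unit is any event, a given type of event or related events only. No confidence interval is specified.

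Two other provisions touch safety data. Section 7.2 adds that "Univariate descriptive statistics and frequency distributions will be calculated, as appropriate for all variables", and Section 8.5 says that "Medical monitoring will include a regular assessment of the number and type of serious adverse events".

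The design also contains a direct tolerability event. Section 3.1 provides that "In case of intolerable side effects, the dose will be reduced to 250mg twice a day". No endpoint in Sections 3.2 to 3.4 and no comparison in Section 7.2 uses it by name.

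**The concern.** The hypothesis is that there is no important harm, whereas the planned test has a null of no difference. Rejecting that null would be evidence against the hypothesis, but failing to reject it is not evidence for it. Without an interval, a criterion or a sample size chosen for safety, the plan offers no inferential route from the adverse-event data to the conclusion that Objective 3 seeks.

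At stake is how a p-value above 0.05 from about 34 pairs is reported. It could be taken as confirming tolerability while the same data remain compatible with a substantial excess on metformin. McNemar also uses only patients observed in both periods. Section 7.1 expects 15% dropout, and Section 4.4.2 itself recognises that early withdrawal may reflect the drug's safety profile. Patients who stop in the first period because of side effects would be absent from the test.

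**Working it through.** **1. The plan's own sample size (Section 7.1).** Inputs: σ 2.5, ρ 0.5, difference 1.25 days, α 0.05 (taken as two-sided).

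- SD of the within-patient difference = 2.5 × √(2 × (1 − 0.5)) = 2.5.
- With n = 34, the noncentrality is 1.25 / (2.5/√34) = 2.92 and the critical t on 33 df is 2.03, which gives power 80.8%. With n = 33 it is 79.5%.
- Inflation for dropout: 34 / 0.85 = 40.

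The statement that a "sample size of 34 patients has 80% power to detect a mean reduction in migraine days of 1.25 days per month" is therefore reproduced. It concerns migraine days only; the documents give no power, event rate or margin for safety.

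**2. What a non-significant result would leave open.** Let b be the number of patients with an event on metformin only, c the number with an event on placebo only, and n the number of pairs.

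- Paired difference d = (b − c)/n
- Wald SE = √(b + c − (b − c)²/n) / n
- 95% CI = d ± 1.96 × SE
- Exact two-sided p = 2 × P(X ≤ min(b, c)), with X binomial(b + c, 0.5)

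For 10 versus 4 with n = 34: d = 6/34 = 17.6 points; SE = √(14 − 36/34)/34 = 10.6 points; CI = 17.6 ± 20.7. Exact p = 2 × 1471/16384 = 0.18. The uncorrected statistic is 36/14 = 2.57, p = 0.11.

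| Pairs | b v c | Difference (points) | Wald 95% CI (points) | Exact p |
|---|---|---|---|---|
| 34 | 6 v 6 | 0 | −20.0 to +20.0 | 1.00 |
| 34 | 8 v 4 | +11.8 | −7.8 to +31.3 | 0.39 |
| 34 | 10 v 4 | +17.6 | −3.1 to +38.4 | 0.18 |
| 40 | 6 v 6 | 0 | −17.0 to +17.0 | 1.00 |

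The splits are illustrations. They need no assumed event rates, only the number of pairs.

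**3. Power, under assumed discordance.** The documents give no adverse-event rates, so these inputs are assumptions. With 34 pairs and two-sided 0.05, power is summed over the binomial distribution of discordant pairs, counting rejections in the direction of excess on metformin.

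| Discordance (metformin only v placebo only) | Excess (points) | Exact | Uncorrected |
|---|---|---|---|
| 20% v 5% | 15 | 29% | 41% |
| 30% v 10% | 20 | 36% | 45% |
| 25% v 5% | 20 | 47% | 58% |
| 25% v 2% | 23 | 71% | 82% |
| 30% v 3% | 27 | 78% | 86% |

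A wider grid used 34 or 40 pairs, within-patient correlation of 0, 0.3 or 0.5, and placebo-period rates of 5–40% for the 10-point excess, 10–40% for 20 points and 10–30% for 15 and 30 points.

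| Excess (points) | Exact | Uncorrected |
|---|---|---|
| 10 | 9–21% | 13–54% |
| 15 | 18–51% | 24–73% |
| 20 | 29–83% | 37–96% |
| 30 | 62–99% | 70–100% |

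Power is low in nearly all scenarios at 10 to 15 points, mixed at 20 and adequate to high at 30.

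**The case against.** Four fair points can be made for the plan.

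- **McNemar is not the whole safety analysis.** A reader might infer that it is, but Section 7.2 also promises descriptive statistics for all variables and Section 8.5 a recurring review of serious events. The worksheet in Section 8.3.1 records description, relationship to the research and severity, so much of a by-type table could be produced already. This stands: McNemar is the only *comparative* analysis. General descriptives do not, however, commit the trial to a paired difference with an interval or to dose-reduction rates.
- **No rule equates non-significance with safety.** A reader might infer that the trial will declare metformin safe if p exceeds 0.05. The documents do not say so; Section 7.2 says only that frequencies will be compared. This stands, and the misreading is a risk rather than a plan. The risk is left open because nothing else inferential is specified for Objective 3.
- **The test does not miss real excesses in general.** A reader might infer that it usually does. That fits excesses of about 10 to 15 points, but not larger ones over a low background. The test version matters too: 5 versus 0 gives p = 0.0625 by the exact test and 0.025 uncorrected, and the plan does not choose. Nor does it fix the event unit, so it cannot be assumed that unrelated events would dilute a drug effect.
- **This is a 40-patient phase II trial sized for efficacy.** Modest safety precision is to be expected, and no safety margin is required of it. This is true, and it favours estimation over a bare test, because an interval shows openly how little has been excluded.

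**Conclusion.** The concern holds in a limited form. Objective 3 pairs a hypothesis of no important harm with a test of difference, without an interval or a criterion, in a trial sized only for migraine days. A non-significant McNemar result could not support that hypothesis: with 34 pairs, even a perfectly balanced 6 versus 6 leaves about 20 points of excess not excluded, and 10 versus 4 leaves up to 38.

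That conclusion follows from the logic of the test and the number of pairs, and holds whichever McNemar version is used. The power figures are weaker evidence, since they rest on assumed rates and depend on the version. The primary efficacy analysis is unaffected.

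**What to change.** In Section 7.2, make estimation the basis for Objective 3:

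- Report the proportion of patients affected on each treatment, and the paired risk difference with its 95% CI, for (a) any adverse event, (b) each main event type, and (c) dose reduction or stopping for side effects.
- State the largest excess on metformin that the interval does not exclude.
- Keep the McNemar p-value as supportive, name the version to be used, and say that non-significance is not evidence of tolerability.
- Define the event unit, and say how patients with data from only one period enter the per-treatment proportions.
- Align the safety hypothesis in Sections 2 and 3.4 with estimation, or pre-specify a tolerability criterion.

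No patients or visits are added. The cost is some wording, one extra table, and a safety statement that will read less favourably than a non-significant p-value.

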7.3 Subject Population(s) for Analysis

All-treated population: Any subject randomized into the study that received at least one dose of study drug employing an intention-to-treat analysis.

8 Safety and Adverse Events

8.1 Definitions

Unanticipated Problems Involving Risk to Subjects or Others (UPIRTSO)

Any unanticipated problem or adverse event that meets the following three criteria:

- Serious: Serious problems or events that results in significant harm, (which may be physical, psychological, financial, social, economic, or legal) or increased risk for the subject or others (including individuals who are not research subjects). These include: (1) death; (2) life threatening adverse experience; (3) hospitalization - inpatient, new, or prolonged; (4) disability/incapacity - persistent or significant; (5) birth defect/anomaly; (6) breach of confidentiality and (7) other problems, events, or new information (i.e.

publications, interim findings, product labeling change) that in the opinion of the local investigator may adversely affect the rights, safety, or welfare of the subjects or others, or substantially compromise the research data, **AND**

- **Unanticipated:** (i.e. unexpected) problems or events are those that are not already described as potential risks in the protocol, consent document, not listed in the Investigator's Brochure, or not part of an underlying disease. A problem or event is "unanticipated" when it was unforeseeable at the time of its occurrence. A problem or event is "unanticipated" when it occurs at an increased frequency or at an increased severity than expected, **AND**
- **Related:** A problem or event is "related" if it is possibly related to the research procedures.

Adverse Event

An untoward or undesirable experience associated with the use of a medical product (i.e. drug, device, biologic) in a patient or research subject.

Serious Adverse Event

Adverse events are classified as serious or non-serious. Serious problems/events can be well defined and include;

- death
- life threatening adverse experience
- hospitalization
- inpatient, new, or prolonged; disability/incapacity
- persistent or significant birth defect/anomaly

and/or per protocol may be problems/events that in the opinion of the sponsor-investigator may have adversely affected the rights, safety, or welfare of the subjects or others, or substantially compromised the research data.

All adverse events that do not meet any of the criteria for serious, should be regarded as **non-serious adverse events**.

Adverse Event Reporting Period

For this study, the study treatment follow-up period is defined as 32 weeks following the initiation of study treatment.

Preexisting Condition

A preexisting condition is one that is present at the start of the study. A preexisting condition should be recorded as an adverse event if the frequency, intensity, or the character of the condition worsens during the study period.

General Physical Examination Findings

At screening, any clinically significant abnormality should be recorded as a preexisting condition. At the end of the study, any new clinically significant findings/abnormalities that meet the definition of an adverse event must also be recorded and documented as an adverse event.

Post-study Adverse Event

All unresolved adverse events should be followed by the investigator until the events are resolved, the subject is lost to follow-up, or the adverse event is otherwise explained. At the last scheduled visit, the investigator should instruct each subject to report, to the investigator, any subsequent event(s) that the subject, or the subject's personal physician, believes might reasonably be related to participation in this study.

Abnormal Laboratory Values

A clinical laboratory abnormality should be documented as an adverse event if active management necessary requiring a change of dosage, or dosing schedule, discontinuation of study treatment or additional follow-up.

Hospitalization, Prolonged Hospitalization or Surgery

Any adverse event that results in hospitalization or prolonged hospitalization should be documented and reported as a serious adverse event unless specifically instructed otherwise in

this protocol. Any condition responsible for surgery should be documented as an adverse event if the condition meets the criteria for an adverse event.

Neither the condition, hospitalization, prolonged hospitalization, nor surgery are reported for diagnostic or elective surgical procedures for a preexisting condition. Surgery should **not** be reported as an outcome of an adverse event if the purpose of the surgery was elective or diagnostic and the outcome was uneventful.

8.2 Recording of Adverse Events

At each contact with the subject, the study team must seek information on adverse events by specific questioning and, as appropriate, by examination. Information on all adverse events should be recorded immediately in the source document, and also in the appropriate adverse event section of the case report form (CRF). All clearly related signs, symptoms, and abnormal diagnostic, laboratory or procedure results should be recorded in the source document.

All adverse events occurring during the study period must be recorded. The clinical course of each event should be followed until resolution, stabilization, or until it has been ultimately determined that the study treatment or participation is not the probable cause. Serious adverse events that are still ongoing at the end of the study period must be followed up, to determine the final outcome. Any serious adverse event that occurs after the study period and is considered to be at least possibly related to the study treatment or study participation should be recorded and reported immediately.

8.3 Reporting of Serious Adverse Events and Unanticipated Problems

When an adverse event has been identified, the study team will take appropriate action necessary to protect the study participant and then complete the Study Adverse Event Worksheet and log. The investigator will evaluate the event and determine the necessary follow-up and reporting required.

8.3.1 Investigator reporting: notifying the Mayo IRB

The investigator will report to the Mayo IRB any UPIRTSOs and Non-UPIRTSOs according to the Mayo IRB Policy and Procedures.

According to Mayo IRB Policy any serious adverse event (SAE) which the Principal Investigator has determined to be a UPIRTSO must be reported to the Mayo IRB as soon as possible but no later than 5 working days after the investigator first learns of the problem/event.

Adverse events will be reported in an adverse event worksheet to be entered in the research database:

- Subject's name:
- Medical record number:
- Disease/histology (if applicable):
- The date the adverse event occurred:
- Description of the adverse event:
- Relationship of the adverse event to the research (drug, procedure, or intervention):
- If the adverse event was expected:
- The severity of the adverse event: (use a table to define severity scale 1-5)
- If any intervention was necessary:
- Resolution: (was the incident resolved spontaneously, or after discontinuing treatment)
- Date of Resolution:

The investigator will review all adverse event reports to determine if specific reports need to be made to the IRB and FDA. The investigator will sign and date the adverse event report when it is reviewed. For this protocol, only directly related SAEs/UPIRTSOs will be reported to the IRB.

8.4 Unmasking/Unblinding Procedures

If unmasking/unblinding of the study drug is needed for subject safety, this will be performed. The study coordinator and the investigational pharmacy will determine if the subject was using

placebo versus active drug. This will be documented in the research database. In most cases, the unmasking/unblinding will be part of managing an SAE, and will be reported with the SAE. However, in cases where unmasking/unblinding was not associated with an SAE, such actions should be reported in a timely manner.

8.5 Medical Monitoring

It is the responsibility of the Principal Investigator to oversee the safety of the study at his/her site. This safety monitoring will include careful assessment and appropriate reporting of adverse events as noted above, as well as the construction and implementation of a site data and safety-monitoring plan (see section 10 “Study Monitoring, Auditing, and Inspecting”). Medical monitoring will include a regular assessment of the number and type of serious adverse events.

9 Data Handling and Record Keeping

9.1 Confidentiality

Information about study subjects will be kept confidential and managed according to the requirements of the Health Insurance Portability and Accountability Act of 1996 (HIPAA).

Those regulations require a signed subject authorization informing the subject of the following:

- What protected health information (PHI) will be collected from subjects in this study
- Who will have access to that information and why
- Who will use or disclose that information
- The rights of a research subject to revoke their authorization for use of their PHI.

In the event that a subject revokes authorization to collect or use PHI, the investigator, by regulation, retains the ability to use all information collected prior to the revocation of subject authorization. For subjects that have revoked authorization to collect or use PHI, attempts should be made to obtain permission to collect at least vital status (long term survival status that the subject is alive) at the end of their scheduled study period.

